### **3.2 Study Endpoints**

#### **3.2.1 Primary Study Endpoints**

Brief Pain Inventory-short form (BPI) pain severity subscale will be used as the primary endpoint at 24h and 48h postoperatively.

#### **3.2.2 Secondary Study Endpoints**

For the secondary endpoint postoperative pain, function (physical), sleep quality, opioid use, quality of recovery, side effects and mood (fatigue) will be assessed.

- 1) BPI (both pain severity and interference) scores at baseline, 1+1, 2+2, and 7+2 days after surgery to assess pain. The BPI severity subscale will be administered post-infusion as well.
- 2) Opioid use will be assessed in the PACU and on postoperative day (POD) 0, 1+1, 2+2, and 7+2. The opioid use and dosage assessment will be assessed through medical records and subject reports.
- 3) Patient-Reported Outcomes Measurement Information System (PROMIS) fatigue scale was developed by the National Institute of Health (NIH) to measure fatigue, an important symptom in postoperative recovery. This scale will be assessed at baseline at POD 1+1, 2+2, and 7+2 days after surgery.
- 4) Patient-Reported Outcomes Measurement Information System (PROMIS) sleep disturbance assesses sleep in postoperative recovery and will be measured at baseline and 7+2 days post-surgery.
- 5) Patient Health Questionnaire-2 (PHQ-2) and Generalized Anxiety Disorder-2 (GAD-2) assess for symptoms of depression and anxiety and will be measured at baseline and POD 7+2.
- 6) Breast Cancer Pain Questionnaire (BCPQ) assesses pain location, frequency and severity as well as sensory disturbance after breast surgery. BCPQ will be completed at 7+2 days post-surgery.
- 7) Quality of Recovery (QoR-15) This scale will be assed at POD 2+2, and 7+2.
- 8) Side effects of study drug administration will be assessed after infusion on POD 0 and on POD 1+1 with a psycho-behavioral questionnaire.

## **4 Study Enrollment and Withdrawal**

### **4.1 Inclusion Criteria**

In order to be eligible to participate in this study, an individual must meet all of the following criteria:

1. Adult women, aged 18 to 80 years old, who will undergo mastectomy.
2. Willing to comply with all study procedures and be available for the duration of the study.
3. Will be scheduled for elective breast surgery for oncologic indication as follows: mastectomy +/- lymph node dissection, prophylactic mastectomy, unilateral or bilateral, with immediate reconstruction
4. No distant metastases.
5. Subject is American Society of Anesthesiologists (ASA) physical status 1, 2, or 3.
6. Subject is medically stable.

#### **4.1.1 Inclusion of Women and Minorities**

Women of all races and ethnic groups are eligible for this trial.

### **4.2 Exclusion Criteria**

An individual who meets any of the following criteria will be excluded from participation in this study:

1. Cognitive impairment (by history) or clinical signs of altered mental status such as confusion, amnesia, disorientation, fluctuating levels of alertness, etc. that may interference with adherence to study procedures and/or participant safety.
2. Past ketamine or phencyclidine misuse or abuse.
3. Schizophrenia or history of psychosis.
4. Known sensitivity or allergy to ketamine.
5. Liver or renal insufficiency.

CONFIDENTIAL

This material is the property of the NYU School of Medicine and Langone Medical Center. Do not disclose or use except as authorized in writing by the study sponsor

6. History of uncontrolled hypertension, chest pain, cardiac arrhythmia, stroke, head trauma, intracranial mass or hemorrhage or pressure, glaucoma, acute globe injury, uncontrolled thyroid disease, porphyria, or any other contraindication to ketamine. Use of lamotrigine, alfentanil, physostigmine, and 4-aminopyridine are contraindicated
7. Pregnancy or nursing women
8. BMI>35.
9. Currently participating in another pain interventional trial.
10. Unwillingness to give informed consent.
11. Non-English speaking patients as QoR-15 and BCPQ have not been validated in all other languages

#### **4.2.1 Vulnerable Subjects**

Vulnerable subject populations will not be included in the study.

#### **4.3 Strategies for Recruitment and Consent**

This study will utilize EPIC to identify prospective subjects.

The privacy of prospective subjects will be protected during the identification process. The research team consists of study surgeons, investigators, treating physicians and research coordinators—they will all have access to EPIC. Study staff members are experienced at consenting patients or prospective subjects for anesthesiology studies, and they include physicians as well as qualified designated team members. Prospective subjects who are eligible for the study will be recruited prior to their surgery date. Eligible patients or prospective subjects will be assessed for capacity to give informed consent by a study team member. Medical status/stability will be addressed by members of the research team. Eligible patients or prospective subjects will be invited to participate in the study. Data will be discarded at least 3 years after close out or 5 years after final reporting, whichever is longer, by deleting from the network.

Any recruitment information sent by email will utilize Send Safe email.

To first screen for eligible subjects, participating study surgeons, investigators, treating physician will review their operating and other schedules on EPIC to identify eligible patients or prospective subjects for study recruitment. Only patients who have agreed to be contacted for future research will be contacted. Research team members will also screen for eligible prospective subjects on all participating physicians' schedules on EPIC and will contact these prospective subjects on their behalf with permission of study surgeons, investigators, treating physician. The subjects' data will be screened to see if they match the study's eligibility criteria. The research team members will search EPIC as many times as needed until all 30 eligible subjects are recruited. Once eligible subjects are identified, recruitment can either be in-person or over the phone.

- 1) Recruited in-person  
A research team member will speak to the eligible subject in-person at NYU Langone Health Perlmutter Cancer Centers, outpatient facilities, and hospitals. The study surgeon may also talk to subjects about the study during their appointment and can refer subjects who are eligible. Surgeons may give potential participants the research subject letter and key information document to introduce the study. Once a subject has been referred, a study team member will call the subject through the "recruitment over the phone" strategies listed below. Should the potential subjects agree, the study team member will provide the subjects with information regarding the next steps for participation. The subject will be given the copy of the informed consent document and given sufficient time to read over the form, and ask all questions. Once all of her questions have been answered, the informed consent will be signed.
- 2) Recruitment over the phone
  - a. The telephone script will be used to communicate the reason they are being contacted and subjects will be asked if they are interested in participating in this specific study. Research

**CONFIDENTIAL**

This material is the property of the NYU School of Medicine and Langone Medical Center. Do not disclose or use except as authorized in writing by the study sponsor

team members will call prospective subjects or arrange a video conference session (WebEx only). The following methods will be implemented to obtain informed consent.

- i. The prospective subject will be emailed a copy of the informed consent via SendSafe and will send back a signed copy of the informed consent form (the prospective subject may print, sign, and scan a physical copy or a signature can be captured electronically on the informed consent form) to a research team member via SendSafe after on-site discussion taking place between study personnel and prospective subject or an initial telephone call or video conference takes place between study personnel and the remote prospective subject.
- ii. The prospective subject will be emailed a copy of the informed consent form via SendSafe after on-site discussion taking place between study personnel and prospective subject or an initial telephone call or video conference takes place between study personnel and the remote prospective subject and the research team member will obtain prospective subject signature in-person on the day of surgery. The prospective subject can print and sign a physical copy and return later in person.
- iii. The subject will remotely receive a link to the informed consent form (after on-site discussion taking place between study personnel and prospective subject or an initial telephone call or video conference takes place between study personnel and the remote prospective subject), sign and return informed consent document through a REDCap link that will be sent via SendSafe e-mail. The REDCap link to the final and approved informed consent document and questionnaires will be IRB approved via a modification before being used.
- iv. In cases of remote consent, before the patient or prospective subject signs the consent, a videoconference or call will be scheduled with the patient or prospective subject to review the informed consent. The study team member will then explain the consent to the prospective subject and ask if the prospective subject has any questions before the prospective subject electronically signs.

Once informed consent is given, the study team member will provide the prospective subjects with information regarding the next steps for participation. Consent may occur up to two months before surgery. Subjects will also be consented no sooner than 2 days before their surgery.

If a subject requests information regarding opting out of further recruitment for all research, subjects will be directed to contact [[contact]](mailto:[contact]) or [name].

The inclusion and exclusion criteria in this study should not have a negative effect on the enrollment of the desired populations. Treatment will take place at the NYU Langone Health Tisch/Kimmel Hospital or NYU Langone Brooklyn under the supervision of the PI. Prospective subjects will receive detailed information regarding this study; its investigational nature, required study procedures, alternative treatments, risks and potential benefits of the study. They will also receive the informed consent document to read. All questions are answered by the PI and qualified research personnel.

Recruitment and consenting will take place in a private area such as exam room (if in person) or remotely (phone call and video conference call) to protect the patient or prospective subject's privacy.

#### **4.4 Registration Procedures**

##### **4.4.1 General Guidelines**

Each patient or prospective subject must sign and date an informed consent form before undergoing any study specific procedure unless a procedure is being performed as part of the patient's standard of care. Enrollment in the study requires that all inclusion and exclusion criteria have been met.

CONFIDENTIAL

This material is the property of the NYU School of Medicine and Langone Medical Center. Do not disclose or use except as authorized in writing by the study sponsor

**4.5 Duration of Study Participation**

For the participation in the study, the study will continue for 7 days or 1 week after surgery. There are 5 visits in total, each visit lasting less than 1 hour.

**4.6 Total Number of Participants and Sites**

Recruitment will take place at NYU Langone Health Perlmutter Cancer Centers, outpatient facilities, and hospitals. Recruitment will end when approximately 30 participants are accrued. It is expected that approximately 50 participants will be enrolled in order to produce 30 evaluable participants.

Target accrual for this study is 30 subjects over 6 months. The sites include NYU Langone Health Tisch/Kimmel Hospital or NYU Langone Hospital Brooklyn.

**4.7 Participant Withdrawal or Termination****4.7.1 Reasons for Withdrawal or Termination**

Participants are free to withdraw from participation in the study at any time upon request for any reason, and without repercussion. The investigator and sponsor have the right to discontinue a subject from study treatment or withdraw a subject from the study at any time. If a subject is discontinued from the study at the discretion of a PI or other delegated individual, the reason for discontinuation procedures will be noted in the subject's research record.

. An investigator may terminate participation in the study if, but are not limited to:

- Subject withdrawal of consent at any time.
- Disease progression.
- Intolerable toxicity.
- Any medical condition that the investigator or sponsor determines may jeopardize the subject's safety if the subject continues treatment with the study drug.
- The investigator or sponsor determines it is in the best interest of the subject.
- Failure of the subject to adhere to protocol procedure requirements.
- Study termination by sponsor.
- Any clinical adverse event (AE) or other medical condition or situation occurs such that continued participation in the study would not be in the best interest of the participant.
- The participant meets an exclusion criterion (either newly developed or not previously recognized) prior to surgery.

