**Criteria for discontinuing study intervention includes but not limited to:**

- Allergic reaction thought to be related to study drug.
- Uncontrolled hypertension, hypotension, or arrhythmia thought to be related to study drug.
- Severe psychomimetic side effects.
- Medical events/logistical reasons not related to study therapy.

Study physician will be responsible for determining whether study interventions will be discontinued, based on his or her clinical judgement. In the case of cardiovascular side effects, if such side effects persist despite treatment based on PACU clinician's decisions, study drug may be discontinued. The reason for the dose discontinuation should be documented.

Psychomimetic side effects will be monitored by study and PACU physicians. Such side effects may be treated with reassurance. If participants continue to complain of anxiety or dysphoria or are agitated, pharmacologic agents (such as benzodiazepines) may be administered based on clinical judgement of PACU clinicians. If psychomimetic side effects are felt to be severe, with severe hallucinations, delusions, or agitation, study drug will be discontinued.

Additionally, in the event of any discontinuation of study intervention, with consent, participants will continue with the completion of remaining study visits.

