#### **6.1.4 Withdrawal/Early Termination Visit/Lost to Follow-up**

Participants are free to withdraw from participation in the study at any time upon request. However, participants should be counseled that they may request stopping the interventional drug but continue to be in the study. They also will be told that follow-up for adverse events is recommended for safety.

Lost to follow-up is defined by the inability to reach a participant after a minimum of two phone calls. All attempts should be documented in the subject's medical records. If it is determined that the subject has died, the site will use permissible local methods to obtain the date and cause of death.

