#### **9.1.1 Sample Size Determination**

This is a pilot study with limited resources so that it is not powered to detect a hypothesized effect size for the BPI subscale at 24 hours and 48 hours. We expect to randomize 15 participants to each arm. With 15 subjects per arm, we have 80% power to test an effect size of 1.1 with a significance level (alpha) of 0.05 using a two-sided Wilcoxon's rank-sum test assuming data are generated from normal distributions.

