### **9.2 Measures to Minimize Bias**

#### **9.2.1 Enrollment/Randomization/Masking Procedures**

The subjects will be randomized in a 1:1 ratio. The treatment subjects will receive 0.6 mg/kg of the study drug, and the control subjects will receive an equal volume of saline. Participants will be randomized with random size permuted blocks, blinded with respect to treatment assignments. [name] will generate the randomization list.

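### Section 4.7.1 does not say whether a drug toxicity ends study participation or only the infusion, so ketamine-arm 24h and 48h pain scores can be lost because of treatment

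*Combined protocol and SAP*

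**What the plan says.** Section 4.7.1 has two lists.

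- **Ending participation.** The first opens with "An investigator may terminate participation in the study if, but are not limited to". Among its grounds are intolerable toxicity and any adverse event that makes further participation not in the participant's best interest.
- **Stopping the intervention.** The second covers drug-related allergic reaction, drug-related uncontrolled blood pressure or arrhythmia, and severe psychomimetic effects. It closes by saying that "in the event of any discontinuation of study intervention, with consent, participants will continue with the completion of remaining study visits".

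Section 6.1.4 points the same way as the second list for participants who ask to withdraw: they are to be told that "they may request stopping the interventional drug but continue to be in the study". Section 4.7.2 promises every effort at safety follow-up after withdrawal or termination, does not mention pain scores, and allows early withdrawals to be replaced. Section 4.6 aims for 30 evaluable participants without defining the term.

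Study drug is one infusion in the PACU on the day of surgery (section 5.1.5). The BPI severity subscale "will be used as the primary endpoint at 24h and 48h postoperatively" (section 3.2.1). Section 1.3 expects no side effects from saline. The physician who gives the drug knows the allocation (sections 3.1 and 5.1.4).

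**The concern.** A severe reaction in the PACU can meet both lists, and they lead to different data. Under the second, the participant completes her visits and gives both primary scores. Under the first, her participation can end on the day of surgery, before either score exists.

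Ending participation spares her no further study drug once the single infusion has stopped, because what remains is questionnaires, opioid-use assessment and adverse-event recording. It does cost the trial her primary outcome. Since drug toxicity is expected on ketamine and not on saline, the loss would fall on one arm and depend on how the participant responded to treatment. Replacement could then fill the place with someone who tolerated the drug, leaving an arm partly selected for tolerance. The choice between the two routes is not reserved to someone unaware of the allocation.

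**Working it through.** **1. The overlap**

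| Event | First list (participation) | Second list (infusion) |
|---|---|---|
| Severe drug toxicity | may end participation | stop drug, complete visits with consent |
| Adverse event, best-interest test met | may end participation | stop drug if it is one of the listed reactions |
| Pain scores afterwards | none promised (4.7.2: safety follow-up only) | collected at the remaining visits |

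No sentence ranks one route above the other.

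**2. What the analyses do with a lost participant**

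Section 10.1 compares the 24h and 48h scores by Wilcoxon rank-sum test and fits an MMRM with baseline pain, treatment, time and their interaction. It defines no analysis population and no rule for missing scores. With no imputation rule, the rank-sum test can use only observed scores. A participant whose participation ends on the day of surgery has a baseline but no 24h or 48h outcome, so she adds nothing to the MMRM treatment contrast.

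**3. The plan's own figure**

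Inputs from section 9.1.1: "With 15 subjects per arm, we have 80% power to test an effect size of 1.1 with a significance level (alpha) of 0.05". The test there is the Wilcoxon rank-sum, two-sided, with scores taken as normal. Allocation from section 9.2.1: "The subjects will be randomized in a 1:1 ratio". Simulating ketamine scores from N(-1.1, 1) and saline scores from N(0, 1), 15 against 15, gives 79.7% power (asymptotic test, 40,000 runs) and 79.8% (exact test, 20,000 runs). The stated 80% is reproduced.

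**4. How likely a loss is**

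The documents give no termination rate, so p = 3% to 5% of the ketamine arm is an assumption. The saline expectation is about zero.

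- At least one loss = 1 - (1 - p)^15. At p = 0.03: 1 - 0.633 = 0.367. At p = 0.05: 1 - 0.463 = 0.537.
- Two or more = 1 - (1 - p)^15 - 15p(1 - p)^14. At p = 0.03: 1 - 0.633 - 0.294 = 0.073. At p = 0.05: 1 - 0.463 - 0.366 = 0.171.
- Expected number = 15p = 0.45 to 0.75.

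**5. What a loss does**

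Power is the exact Wilcoxon test at 1.1 SD with 15 - k against 15. The bias column assumes no true effect and that the k highest ketamine scores are the ones lost (40,000 runs). The last column is the resulting rejection rate of the nominal two-sided 5% test.

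| Ketamine participants lost (k) | Power | Worst-case shift in arm difference | Type I error |
|---|---|---|---|
| 0 | 79.8% | 0 | 5% (nominal) |
| 1 | 78.0% | -0.12 SD | 6% |
| 2 | 76.4% | -0.23 SD | 9.5% |
| 3 | 74.7% | -0.33 SD | 14% |

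If the lowest scores are lost instead, the shift is about the same size in the other direction. If the lost scores are typical of the arm, there is no shift and only the power cost remains.

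**The case against.** The strongest reply is that the specific rule governs the general one. For severe hallucinations, delusions or agitation, section 4.7.1 and section 6.3 both say the study drug is to be stopped, and section 4.7.1 then says visits continue. That is an instruction, while the first list is only a permission. The adverse-event ground also carries a best-interest test, which would seldom be met when only questionnaires remain. This is probably how most staff would read it, and it argues for a low termination rate. It does not close the gap: the toxicity ground carries no such test, the first list is not made subject to the second, and section 4.7.2 provides for replacement.

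A second reply is that this is a 30-person pilot which says it is not powered. That stands for the loss of power, which is small. It does not answer selective loss, which affects the estimate itself.

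Some stronger readings are tempting, but the documents do not support them:

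- **The lists contradict each other outright.** They do not. One is permissive and concerns participation; the other concerns the infusion. The fault is an overlap left unresolved.
- **The same problem covers non-adherence and disease progression.** The first list does include "Failure of the subject to adhere to protocol procedure requirements" and progression, but the second names neither, and nothing ties either to ketamine within seven days.
- **Section 6.1.4 binds the investigator.** It concerns participants who ask to stop. It shows an intent to keep follow-up and no more.
- **Safety follow-up is lost.** Section 4.7.2 promises effort to capture events. Section 7.5 follows unresolved events and records new ones for 7 days (non-serious) or 30 days (serious) after participation ends.
- **About 12% of the ketamine arm would be lost.** Section 1.3 gives that figure for emergence reactions of any kind, citing the package insert. It is not a rate of severe reactions or of terminations. Applying it (15 x 0.12 = 1.8 participants) would overstate the case.

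**Conclusion.** The point holds for drug toxicity and adverse events. As written, the plan permits treatment-related loss of primary scores in the ketamine arm, and nothing in the analysis section repairs it.

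The size is modest. With an assumed 3-5% termination rate, losing at least one of 15 is roughly as likely as not (37-54%), while losing two or more is less likely (7-17%). Power drops by about 2 points per participant. The 0.23 SD shift for two losses is a bound, reached only if the lost scores are the two highest; the documents do not say in which direction a real loss would run. It is worth correcting because the trial seeks a preliminary estimate of efficacy from 15 per arm, where one or two selectively missing scores matter and the remedy is nearly free.

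**What to change.** Reconcile the two lists in section 4.7.1 with sections 4.7.2 and 6.1.4 so that stopping study drug and ending participation are clearly separate. State that a randomized participant whose study drug is stopped for toxicity or an adverse event is still asked, with consent, for BPI at Visits 3, 4 and 5. State in sections 4.7.2 and 10.1 that she is analysed in her assigned arm and is not replaced.

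This extends the plan's own rule for discontinued infusions. It sets no new limits on when the infusion is stopped. It also draws up no closed list of permitted reasons for ending participation, which would remove the investigator's best-interest judgement. Both decisions stay with the clinicians.

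The cost is the rewording of a few paragraphs, with no added visits. The small downside is a few more questionnaire contacts with participants who had a bad reaction, any of whom may refuse.
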